### 17.3. Appendix III – Safety Outcomes of Interest

All codes are ICD-10 diagnosis codes; all outcomes will be defined based on the presence of a single code unless otherwise specified. In order to qualify as an outcome, the outcome-specific codes must be identified during emergency department visits, inpatient hospitalizations, or outpatient visits, as detailed in [Table 2](#). Outpatient visits are defined through physician evaluation and management codes ([Section 17.2.3](#)).

\* Outcome codes marked with an asterisk are based on COVID-19 vaccine studies conducted as part of the FDA’s CBER BEST system.

- Acute disseminated encephalomyelitis (ADEM)\*
  - G04.00 – Acute disseminated encephalitis and encephalomyelitis, unspecified
- Anaphylaxis\*
  - T80.52XA – Anaphylactic reaction due to vaccination, initial encounter
  - T78.2XXA – Anaphylactic shock, unspecified, initial encounter
- Bell's palsy\*
  - G51.0 – Bell’s palsy
  - G51.8 – Other disorders of facial nerve
  - G51.9 – Disorder of facial nerve, unspecified
- Cerebral venous sinus thrombosis (CVST)
  - I67.6 – Nonpyogenic thrombosis of intracranial venous system
  - I63.6 – Cerebral infarction due to cerebral venous thrombosis, nonpyogenic
- Convulsions/seizures (non-febrile)
  - G40.001 – Localization-related (focal) (partial) idiopathic epilepsy and epileptic syndromes with seizures of localized onset, not intractable, with status epilepticus
  - G40.009 – Localization-related (focal) (partial) idiopathic epilepsy and epileptic syndromes with seizures of localized onset, not intractable, without status epilepticus
  - G40.011 – Localization-related (focal) (partial) idiopathic epilepsy and epileptic syndromes with seizures of localized onset, intractable, with status epilepticus
  - G40.019 – Localization-related (focal) (partial) idiopathic epilepsy and epileptic syndromes with seizures of localized onset, intractable, without status epilepticus
  - G40.101 – Localization-related (focal) (partial) symptomatic epilepsy and epileptic syndromes with simple partial seizures, not intractable, with status epilepticus

090177e1a5be86fe\Approved\Approved On: 19-Mar-2026 15:57 (GMT)

- G40.109 – Localization-related (focal) (partial) symptomatic epilepsy and epileptic syndromes with simple partial seizures, not intractable, without status epilepticus

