  - N04.5 Nephrotic syndrome with diffuse mesangiocapillary glomerulonephritis
  - N04.3 Nephrotic syndrome with diffuse mesangial proliferative glomerulonephritis
  - N04.4 Nephrotic syndrome with diffuse endocapillary proliferative glomerulonephritis
  - N05.A Unspecified nephritic syndrome with C3 glomerulonephritis
  - N05.7 Unspecified nephritic syndrome with diffuse crescentic glomerulonephritis
  - N05.2 Unspecified nephritic syndrome with diffuse membranous glomerulonephritis
  - N05.5 Unspecified nephritic syndrome with diffuse mesangiocapillary glomerulonephritis
  - N03.A Chronic nephritic syndrome with C3 glomerulonephritis
  - N03.7 Chronic nephritic syndrome with diffuse crescentic glomerulonephritis
  - N03.2 Chronic nephritic syndrome with diffuse membranous glomerulonephritis
  - N03.5 Chronic nephritic syndrome with diffuse mesangiocapillary glomerulonephritis

- N00.A Acute nephritic syndrome with C3 glomerulonephritis
- N00.2 Acute nephritic syndrome with diffuse membranous glomerulonephritis
- N00.5 Acute nephritic syndrome with diffuse mesangiocapillary glomerulonephritis
- N00.7 Acute nephritic syndrome with diffuse crescentic glomerulonephritis
- N07.A Hereditary nephropathy, not elsewhere classified with C3 glomerulonephritis
- N02.7 Recurrent and persistent hematuria with diffuse crescentic glomerulonephritis
- N02.A Recurrent and persistent hematuria with C3 glomerulonephritis
- Guillain-Barré syndrome\*
  - G61.0 – Guillain-Barré syndrome
- Herpes zoster
  - B02.\* Zoster [herpes zoster]
- Immune-mediated myositis
  - G72.41 – Inclusion body myositis [IBM]
  - M33 – Dermatopolymyositis
    - M33.0 – Juvenile dermatomyositis
      - M33.00 – Juvenile dermatomyositis, organ involvement unspecified
      - M33.01 – Juvenile dermatomyositis with respiratory involvement
      - M33.02 – Juvenile dermatomyositis with myopathy
      - M33.03 – Juvenile dermatomyositis without myopathy
      - M33.09 – Juvenile dermatomyositis with other organ involvement
    - M33.1 – Other dermatomyositis
      - M33.10 – Other dermatomyositis, organ involvement unspecified
      - M33.11 – Other dermatomyositis with respiratory involvement
      - M33.12 – Other dermatomyositis with myopathy
      - M33.13 – Other dermatomyositis without myopathy
      - M33.19 – Other dermatomyositis with other organ involvement
    - M33.2 – Polymyositis
      - M33.20 – Polymyositis, organ involvement unspecified

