      - M33.21 – Polymyositis with respiratory involvement
      - M33.22 – Polymyositis with myopathy

- M33.29 – Polymyositis with other organ involvement
- M33.9 – Dermatopolymyositis, unspecified
- M33.90 – Dermatopolymyositis, unspecified, organ involvement unspecified
- M33.91 – Dermatopolymyositis, unspecified with respiratory involvement
- M33.92 – Dermatopolymyositis, unspecified myopathy
- M33.93 – Dermatopolymyositis, unspecified without myopathy
- M33.99 – Dermatopolymyositis, unspecified with other organ involvement
- G72.41 – Other and unspecified myopathies
- G72.0 – Drug-induced myopathy
- G72.2 – Myopathy due to other toxic agents
- G72.41 – Inflammatory and immune myopathies, not elsewhere
- G72.49 – Other inflammatory and immune myopathies, not elsewhere classified
- G72.8 – Other specified myopathies
- G72.9 – Myopathy, unspecified
- G73.7 – Myopathy in diseases classified elsewhere
- M36.0 – Dermato(poly)myositis in neoplastic disease
- I42.7 – Cardiomyopathy due to drug and external agent
- I42.9 – Cardiomyopathy, unspecified
- I43 – Cardiomyopathy in diseases classified elsewhere
- I42 – Cardiomyopathy
- M79.1 – Myalgia
- M79.7 – Fibromyalgia
- I42.5 – Other restrictive cardiomyopathy
- I42.8 – Other cardiomyopathies
- Immune thrombocytopenia\*
  - D69.3 – Immune thrombocytopenic purpura
- Kawasaki disease\*
  - M30.3 – Mucocutaneous lymph node syndrome [Kawasaki]
- Multi inflammatory syndrome (in children and adults)\*
  - U07.1 – COVID-19 **and one of the following:**
  - M35.8 – Other specified systemic involvement of connective tissue

- M35.81 – Multisystem inflammatory syndrome
- M35.89 – Other specified systemic involvement of connective tissue
- Multiple sclerosis
  - G35 – Multiple sclerosis
- Myocardial infarction\*
  - I21.01 – ST elevation (STEMI) myocardial infarction involving left main coronary artery
  - I21.02 – ST elevation (STEMI) myocardial infarction involving left anterior descending coronary artery
  - I21.09 – ST elevation (STEMI) myocardial infarction involving other coronary artery of anterior wall
  - I21.11 – ST elevation (STEMI) myocardial infarction involving right coronary artery
  - I21.19 – ST elevation (STEMI) myocardial infarction involving other coronary artery of inferior wall
  - I21.21 – ST elevation (STEMI) myocardial infarction involving left circumflex coronary artery
  - I21.29 – ST elevation (STEMI) myocardial infarction involving other sites

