
090177e1a5be86fe\Approved\Approved On: 19-Mar-2026 15:57 (GMT)

- I31.0 Chronic adhesive pericarditis
- I31.1 Chronic constrictive pericarditis
- I31.2 Hemopericardium, not elsewhere classified
- I31.3 Pericardial effusion (noninflammatory)
- I31.4 Cardiac tamponade
- I31.8 Other specified diseases of pericardium
- I31.9 Disease of pericardium, unspecified
- I33.0 Acute and subacute infective endocarditis
- I33.9 Acute and subacute endocarditis, unspecified
- I34.0 Nonrheumatic mitral (valve) insufficiency
- I34.1 Nonrheumatic mitral (valve) prolapse
- I34.2 Nonrheumatic mitral (valve) stenosis
- I34.8 Other nonrheumatic mitral valve disorders
- I34.9 Nonrheumatic mitral valve disorder, unspecified
- I35.0 Nonrheumatic aortic (valve) stenosis
- I35.1 Nonrheumatic aortic (valve) insufficiency
- I35.2 Nonrheumatic aortic (valve) stenosis with insufficiency
- I35.8 Other nonrheumatic aortic valve disorders
- I35.9 Nonrheumatic aortic valve disorder, unspecified
- I36.0 Nonrheumatic tricuspid (valve) stenosis
- I36.1 Nonrheumatic tricuspid (valve) insufficiency
- I36.2 Nonrheumatic tricuspid (valve) stenosis with insufficiency
- I36.8 Other nonrheumatic tricuspid valve disorders
- I36.9 Nonrheumatic tricuspid valve disorder, unspecified

090177e1a5be86fe\Approved\Approved On: 19-Mar-2026 15:57 (GMT)

- I37.0 Nonrheumatic pulmonary valve stenosis
- I37.1 Nonrheumatic pulmonary valve insufficiency
- I37.2 Nonrheumatic pulmonary valve stenosis with insufficiency
- I37.8 Other nonrheumatic pulmonary valve disorders
- I37.9 Nonrheumatic pulmonary valve disorder, unspecified
- I38 Endocarditis, valve unspecified
- I39 Endocarditis and heart valve disorders in diseases classified elsewhere
- I40.0 Infective myocarditis
- I40.1 Isolated myocarditis
- I40.8 Other acute myocarditis
- I40.9 Acute myocarditis, unspecified
- I41 Myocarditis in diseases classified elsewhere
- I42.0 Dilated cardiomyopathy
- I42.1 Obstructive hypertrophic cardiomyopathy
- I42.2 Other hypertrophic cardiomyopathy
- I42.3 Endomyocardial (eosinophilic) disease
- I42.4 Endocardial fibroelastosis
- I42.5 Other restrictive cardiomyopathy
- I42.6 Alcoholic cardiomyopathy
- I42.7 Cardiomyopathy due to drug and external agent
- I42.8 Other cardiomyopathies
- I42.9 Cardiomyopathy, unspecified
- I43 Cardiomyopathy in diseases classified elsewhere
- I44.0 Atrioventricular block, first degree

- I44.1 Atrioventricular block, second degree
- I44.2 Atrioventricular block, complete

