#### 17.4.1.8. Kidney Disorders

##### 17.4.1.8.1. ICD-10-CM Codes

N00.0	Acute nephritic syndrome with minor glomerular abnormality
N00.1	Acute nephritic syndrome with focal and segmental glomerular lesions
N00.2	Acute nephritic syndrome with diffuse membranous glomerulonephritis
N00.3	Acute nephritic syndrome with diffuse mesangial proliferative glomerulonephritis
N00.4	Acute nephritic syndrome with diffuse endocapillary proliferative glomerulonephritis
N00.5	Acute nephritic syndrome with diffuse mesangiocapillary glomerulonephritis
N00.6	Acute nephritic syndrome with dense deposit disease
N00.7	Acute nephritic syndrome with diffuse crescentic glomerulonephritis
N00.8	Acute nephritic syndrome with other morphologic changes
N00.9	Acute nephritic syndrome with unspecified morphologic changes
N01.0	Rapidly progressive nephritic syndrome with minor glomerular abnormality
N01.1	Rapidly progressive nephritic syndrome with focal and segmental glomerular lesions
N01.2	Rapidly progressive nephritic syndrome with diffuse membranous glomerulonephritis
N01.3	Rapidly progressive nephritic syndrome with diffuse mesangial proliferative glomerulonephritis
N01.4	Rapidly progressive nephritic syndrome with diffuse endocapillary proliferative glomerulonephritis

090177e1a5be86fe\Approved\Approved On: 19-Mar-2026 15:57 (GMT)

- N01.5 Rapidly progressive nephritic syndrome with diffuse mesangiocapillary glomerulonephritis
- N01.6 Rapidly progressive nephritic syndrome with dense deposit disease
- N01.7 Rapidly progressive nephritic syndrome with diffuse crescentic glomerulonephritis
- N01.8 Rapidly progressive nephritic syndrome with other morphologic changes
- N01.9 Rapidly progressive nephritic syndrome with unspecified morphologic changes
- N02.0 Recurrent and persistent hematuria with minor glomerular abnormality
- N02.1 Recurrent and persistent hematuria with focal and segmental glomerular lesions
- N02.2 Recurrent and persistent hematuria with diffuse membranous glomerulonephritis
- N02.3 Recurrent and persistent hematuria with diffuse mesangial proliferative glomerulonephritis
- N02.4 Recurrent and persistent hematuria with diffuse endocapillary proliferative glomerulonephritis
- N02.5 Recurrent and persistent hematuria with diffuse mesangiocapillary glomerulonephritis
- N02.6 Recurrent and persistent hematuria with dense deposit disease
- N02.7 Recurrent and persistent hematuria with diffuse crescentic glomerulonephritis

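### Immune-mediated myositis can be met by a single code for myalgia, fibromyalgia, cardiomyopathy or non-inflammatory myopathy: 13 of its 40 listed codes do not name inflammatory or immune muscle disease

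*Protocol*

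**What the plan says.** Section 9.3.2 names immune-mediated myositis and glomerulonephritis among the pre-specified outcomes of both phases. It prefers validated claims algorithms where possible. Section 17.3 sets the rule that "all outcomes will be defined based on the presence of a single code unless otherwise specified". Nothing further is specified for myositis.

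Table 2 gives myositis a clean period of days -365 to 0, a risk interval of days 1 to 28, and inpatient or outpatient care.

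The myositis list begins with the dermatomyositis and polymyositis codes (M33). It goes on to "G72.0 – Drug-induced myopathy", other toxic and unspecified myopathies, "I42.9 – Cardiomyopathy, unspecified" with further I42 and I43 codes, "M79.1 – Myalgia" and "M79.7 – Fibromyalgia".

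The glomerulonephritis list has 25 codes, none from family N01, and includes "N07.A Hereditary nephropathy, not elsewhere classified with C3 glomerulonephritis". The kidney covariate list (Section 17.4.1.8.1) does contain N01 codes, for example "Rapidly progressive nephritic syndrome with diffuse crescentic glomerulonephritis".

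Neither list carries the asterisk that marks codes taken from the FDA CBER BEST studies.

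**The concern.** Myositis is one of four vaccine adverse event reports that Section 7 cites as background to the study. Under the single-code rule, a correctly coded outpatient visit for muscle pain counts as a myositis case. The protocol itself treats most of the cardiomyopathy codes as heart disease: "I42.9 Cardiomyopathy, unspecified" stands in Section 17.4.1.5.1, as do I42.5, I42.7, I42.8 and I43.

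Three things follow:

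- **The ratio mixes diseases.** A real myositis effect can be hidden, or a change in the other codes can be reported as myositis.
- **Eligible people are lost.** Outcome-specific exclusions use the same definition (Section 9.2.2.2), so a myalgia code in the prior year removes the person. Section 9.7.2.1 removes the matched comparators of excluded individuals as well.
- **Cohort follow-up stops early.** It ends at the first qualifying code (Section 9.2.5.2), so a later true myositis is not seen.

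For glomerulonephritis the issue is narrower: codes that the protocol labels as the disease are missing from its outcome list.

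**Working it through.** The protocol states no figure for this point, so there is none to reproduce. The check is a code count and a dilution formula.

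**1. Myositis code count (Section 17.3).** There are 42 lines. G72.41 appears three times under three different labels, so there are 42 - 2 = 40 unique codes.

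| Group | Codes | Count |
|---|---|---|
| Names inflammatory or immune muscle disease | M33 and its subcodes (24), M36.0, G72.41, G72.49 | 27 |
| Pain syndromes | M79.1, M79.7 | 2 |
| Cardiomyopathy | I42, I42.5, I42.7, I42.8, I42.9, I43 | 6 |
| Drug or toxic myopathy | G72.0, G72.2 | 2 |
| Other, unspecified or secondary myopathy | G72.8, G72.9, G73.7 | 3 |

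The last four rows sum to 13, and 27 + 13 = 40.

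**2. Dilution.** Let p be the share of true myositis among reference events (control window or comparator cohort). The protocol gives no value, so p is assumed. In general,

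RR_obs = p × RR_true + (1 - p) × RR_other.

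If the other codes are unaffected by vaccination (RR_other = 1), this becomes RR_obs = 1 + p(RR_true - 1). The true ratio needed to read 3.0 is then 1 + 2/p.

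| Assumed p | True RR 3 reads | True RR 5 reads | True RR needed to read 3.0 |
|---|---|---|---|
| 0.01 | 1.02 | 1.04 | 201 |
| 0.10 | 1.20 | 1.40 | 21 |
| 0.50 | 2.0 | 3.0 | 5 |
| 1.00 | 3.0 | 5.0 | 3 |

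The signal rule in Section 9.3.2 needs a ratio above 3.0 (with P < 0.01). Even at p = 0.50, a true fivefold risk only reaches that line.

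**3. The opposite direction.** Set RR_true = 1 and let 90% of reference events be non-myositis codes. The ratio exceeds 3.0 once RR_other passes 1 + 2/0.9 = 3.22, with no myositis effect at all.

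**4. Glomerulonephritis.** In the kidney covariate list, families N00 to N06 with endings .2, .3, .4, .5 and .7 are labelled glomerulonephritis: 7 × 5 = 35 acquired codes. The outcome list contains 18 of them: three from N00, one from N02, three from N03, five from N04, three from N05 and three from N06. Its other seven codes end in .A.

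The 17 missing codes (17/35 = 49%) are N00.3-.4, N01.2-.5 and .7, N02.2-.5, N03.3-.4, N05.3-.4 and N06.2-.3. A person whose only baseline code is from N01 also passes the clean period and could later count as incident under a listed code.

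If sensitivity is s and equal in both windows or cohorts, incidence is multiplied by s and SE(log RR) by 1/√s. For assumed s of 0.9, 0.7 and 0.5, incidence is understated by 10%, 30% and 50%, and the standard error is multiplied by 1.05, 1.20 and 1.41.

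**The case against.** **Mitigations in the protocol.** The 365-day clean period removes many people with chronic fibromyalgia or cardiomyopathy. Record review is required for a subset after an interim self-controlled signal and is allowed elsewhere (Section 9.3.2). Section 9.9 warns that a code is not confirmation of disease. These points have some force. The clean period reduces prevalent noise, and review limits the harm of a false signal. They do not cure the definition: new myalgia codes still count, dilution suppresses the signal that would trigger review, and Section 9.9 concerns miscoding and rule-out codes, whereas here a correctly coded myalgia counts.

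**Deferral to another document.** Section 7 calls this a combined protocol and statistical analysis plan, and Annex 1 lists no standalone documents.

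**Breadth as a choice.** Keeping G72.8, G72.9 and G73.7 is a trade of specificity for sensitivity that can be argued. That stands, and those codes belong in a sensitivity analysis.

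**Glomerulonephritis.** A reader might infer that this list also fails to measure its disease. It does not support that: all 25 codes name glomerulonephritis, and six are crescentic forms (N00.7, N02.7, N03.7, N04.7, N05.7, N06.7). A count of 22 missing from 40 is also tempting, but it includes five hereditary N07 codes that would not be added. A share of codes is not a share of cases, and the protocol gives no code frequencies.

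**Conclusion.** The myositis definition is wrong as written and should be corrected before its results are interpreted. The code count and the single-code rule can be checked directly in the protocol, and no section cures them. The direction of the dilution holds for any p below 1 if the other codes are unaffected and the true ratio is above 1. Its size rests entirely on the assumed p: a true ratio of 5 reads 1.04 to 3.0 for p from 0.01 to 0.50.

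Two stronger readings are not supported:

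- A reader might assume background rates, find an observed ratio of practically 1 and treat that as established. The protocol gives no incidence for any of these codes.
- A reader might infer that post-vaccination muscle pain will produce a false signal, or that acute glomerulonephritis is the form a vaccine effect would take. The protocol gives no source for either. The first is possible only as shown in step 3.

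The glomerulonephritis list is a separate, less serious matter of completeness. It understates incidence and loses precision, and it does not by itself bias the ratio if the loss is equal across windows or cohorts.

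**What to change.** **Myositis, by dated amendment to Section 17.3:**

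- Restrict the primary definition to M33.*, M36.0, G72.41 and G72.49. Remove at least the myalgia, fibromyalgia, cardiomyopathy and drug or toxic myopathy codes.
- Reconcile the three G72.41 labels and state which condition is meant.
- Report the current broad list, including G72.8, G72.9 and G73.7, as a sensitivity analysis.

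No separate change is needed for the clean period, because Section 9.2.2.2 already ties it to the outcome definition.

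**Glomerulonephritis:** add the 17 codes listed above, or justify leaving them out, and reconsider hereditary N07.A.

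**Cost:** an appendix edit and a rerun. Myositis will have fewer events and wider intervals. With equal windows, an exact two-sided P below 0.01 needs at least eight events, all in the risk window (2 × 0.5^8 = 0.0078; seven events give 2 × 0.5^7 = 0.0156). The change also comes late. Version 3.0 is dated 18 March 2026, after the planned interim report (30 June 2024) and the planned end of data collection (31 August 2025). It must be disclosed as a post-data change of definition, with results under both lists.

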### 9.3.1.2. Comparator Cohort

The Phase 2 cohort study will include comparators with no recorded vaccination for the COMIRNATY 2023-2024 Formula. To improve comparability with the COMIRNATY 2023-2024 Formula vaccinated cohort, patients included in the comparator cohort will be required to have a code indicative of a healthcare encounter, including one of the following:

- Presence of a code for a vaccine other than the COMIRNATY 2023-2024 Formula;
- Presence of a code indicative of an outpatient healthcare encounter.

Codes relating to other vaccines or outpatient visits are provided in [Annex 2 \(Appendix II\)](#).

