**Table 2. Clean periods and risk intervals for safety outcomes of interest**

Outcome	Clean Period*	Vaccine Risk Interval*	Care Setting**
Acute disseminated encephalomyelitis	Days -28 to -1	Days 0 to 21	IP
Anaphylaxis	Days -30 to -1	Days 0 to 1	IP, ED
Bell's palsy	Days -183 to 0	Days 1 to 42	IP, OP
Cerebral venous sinus thrombosis	Days -365 to 0	Days 1 to 28	IP, OP
Convulsions/seizures, non-febrile	Days -42 to -1	Days 0 to 21	IP, OP
Encephalomyelitis	Days -183 to 0	Days 1 to 42	IP
Glomerulonephritis	Days -365 to 0***	Days 1 to 42***	IP, OP
Guillain-Barré syndrome	Days -365 to 0	Days 1 to 42	IP-primary position only
Herpes zoster	Days -270 to 0	Days 1 to 30	IP, OP
Immune-mediated myositis	Days -365 to 0***	Days 1 to 28	IP, OP
Immune thrombocytopenia	Days -365 to 0	Days 1 to 42	IP, OP
Kawasaki disease	Days -365 to 0	Days 1 to 21	IP, OP
Multi inflammatory syndrome	Days -365 to 0	Days 1 to 42	IP, ED
Multiple sclerosis	Days -365 to 0	Days 1 to 42***	IP, OP
Myocardial infarction	Days -365 to 0	Days 1 to 28	IP
Myocarditis/pericarditis	Days -365 to 0	Days 1 to 21	IP, OP

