### 9.3.2.1. Outcome-Specific Risk and Control Periods

The SCRI design ([Section 9.1.1](#)) requires that clean periods, risk intervals, washout periods, and control intervals be specified for every study outcome. The lengths of the clean periods and risk intervals are listed in [Table 2](#). The washout period for all outcomes will begin immediately after the end of the risk interval and continue for 30 days ([Akpandak et al., 2022](#)); the control period will follow the washout period and be equivalent in length to the risk interval. Interval lengths were determined based on prior vaccine literature, including COVID-19 vaccine studies conducted as part of the FDA’s Center for Biologics Evaluation and Research (CBER) Biologics Effectiveness and Safety (BEST) System ([Akpandak et al., 2022](#); [Barda et al., 2021](#); [CBER, 2021](#); [Joy et al., 2023](#); [Klein et al., 2021](#); [Liu et al., 2023](#); [Martin et al., 2021](#); [McCarthy et al., 2013](#); [Wack et al., 2021](#)).

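### Multi inflammatory syndrome counts only when COVID-19 is also coded, so an increase confined to cases without a COVID-19 code cannot be detected in either design

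*Protocol*

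**What the plan says.** Section 17.3 (Appendix III) sets a default for safety outcomes: "all outcomes will be defined based on the presence of a single code unless otherwise specified". Multi inflammatory syndrome is an express exception. Its entry reads "U07.1 – COVID-19 and one of the following", and the codes beneath it are M35.8, M35.81 and M35.89. One of these is "M35.81 – Multisystem inflammatory syndrome", the code that names the outcome.

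The entry carries an asterisk, which the appendix explains: "Outcome codes marked with an asterisk are based on COVID-19 vaccine studies conducted as part of the FDA’s CBER BEST system".

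Table 2 gives the clean period, risk interval and care setting: "Multi inflammatory syndrome Days -365 to 0 Days 1 to 42 IP, ED". For the SCRI, Section 9.3.2.1 adds that "The washout period for all outcomes will begin immediately after the end of the risk interval and continue for 30 days" and that "the control period will follow the washout period and be equivalent in length to the risk interval". For the cohort, Section 9.3.1.2 states: "The Phase 2 cohort study will include comparators with no recorded vaccination for the COMIRNATY 2023-2024 Formula". Section 9.7.2.3 shows that this group includes recipients of the Moderna and Novavax 2023-2024 vaccines.

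The appendix does not say how close in time U07.1 and the M35.8x code must be.

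**The concern.** Section 9.3.2 lists the outcome as multi inflammatory syndrome in children and adults, with no mention of infection. The objectives in Section 8 concern the incidence of listed events after vaccination. The code rule measures something narrower: the syndrome with a recorded COVID-19 diagnosis. In the Section 17.3 list, no other safety outcome requires a COVID-19 code.

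Two things follow. A recipient with M35.81 and no U07.1 contributes no event, so an increase limited to such patients leaves the rate ratio unchanged. The cases that do count depend on how much COVID-19 occurs, and vaccination may lower that.

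Nothing else in the protocol repairs this. Record review under Section 9.3.2 confirms events already counted, after a signal, and cannot recover cases that the code rule leaves out. History of SARS-CoV-2 infection in the propensity score is a baseline variable and says nothing about infection during follow-up. Section 9.9 does not mention the issue. Section 7 describes the document as a combined protocol and SAP, so the code list is settled here. A null or low ratio for this outcome could be read as more reassuring than it is.

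**Working it through.** The protocol gives no expected count, rate or power for this outcome, so there is no stated figure to reproduce. The check has four parts.

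**1. Counting rule.** Take a recipient admitted on day 20, inside the day 1 to 42 risk interval, with M35.81.

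- With U07.1: counted in the SCRI and the cohort.
- Without U07.1: counted in neither.

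The share of uncoded cases that is counted is 0 by definition, whatever their number.

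**2. Cohort ratio under the current definition.** The inputs below are not in the protocol and are assumptions.

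- v: reduction in COVID-19 incidence from vaccination, varied from 0.1 to 0.7.
- m: share of comparators with another, equally protective COVID-19 vaccine, varied from 0 to 1.
- Counted cases are proportional to COVID-19 incidence, and vaccination has no direct effect on them.

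Then RR = (1 − v)/(1 − mv).

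| v | m = 0 | m = 0.3 | m = 1 |
|---|---|---|---|
| 0.1 | 0.90/1 = 0.90 | 0.90/0.97 = 0.93 | 1.00 |
| 0.3 | 0.70/1 = 0.70 | 0.70/0.91 = 0.77 | 1.00 |
| 0.5 | 0.50/1 = 0.50 | 0.50/0.85 = 0.59 | 1.00 |
| 0.7 | 0.30/1 = 0.30 | 0.30/0.79 = 0.38 | 1.00 |

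The m = 0 column describes comparators with no COVID-19 vaccine. The m = 1 column describes the secondary comparison with Moderna or Novavax recipients.

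**3. SCRI.** Risk days are 1 to 42, washout days 43 to 72 and control days 73 to 114. Both windows have 42 days and both follow vaccination. Assume flat COVID-19 incidence, no protection on days 1 to 14, protection v on days 15 to 42, and protection v_c in the control window. Then RR = [(14 + 28(1 − v))/42]/(1 − v_c).

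- v = v_c = 0.3: 0.800/0.7 = 1.14
- v = v_c = 0.5: 0.667/0.5 = 1.33
- v = v_c = 0.7: 0.533/0.3 = 1.78
- v = 0.5 waning to v_c = 0.3: 0.667/0.7 = 0.95
- v = 0.7 waning to v_c = 0.4: 0.533/0.6 = 0.89

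The shift can go either way.

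**4. What a wider definition would show in the cohort.** Let vaccination add M35.81 cases without U07.1 at e times the unprotected baseline rate, and assume comparators have no such cases. Counting them gives RR = (1 − v + e)/(1 − mv). The current definition stays at (1 − v)/(1 − mv).

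- v = 0.5, m = 0, e = 2: 2.50 when counted, 0.50 under the current rule.
- v = 0.3, m = 0, e = 0.5: 1.20 when counted, 0.70 under the current rule.
- e = 0: the two definitions give the same ratio.

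**The case against.** The definition is deliberate. It is marked as coming from the FDA CBER BEST studies, and Section 9.3.2 prefers validated algorithms where possible. The rationale and performance of the source algorithm cannot be seen from the protocol, and the document does not contradict itself here. Section 7 lists the concerns behind the study without naming this syndrome, and nothing in the protocol shows that vaccine-caused cases without infection occur. All of this stands. It is a reason to keep the definition, but it does not let the definition count cases that it excludes.

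A reader might infer that any protection against COVID-19 makes the vaccine look protective throughout. The documents do not support that. Both SCRI windows follow vaccination, so protection partly cancels and the direction depends on onset, waning and COVID-19 incidence. Against equally protected Moderna or Novavax recipients there is no shift. In the primary comparison the group is mixed. Section 9.2.5.2 also lists no censoring at a later COVID-19 vaccination for comparators who entered on another kind of encounter, which would weaken the contrast further.

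A reader might also infer that a case without infection can never be counted. That is exact only for cases without a U07.1 code. Section 9.9 accepts that a diagnosis code may be wrong or entered as a rule-out, and no time link between the two codes is set.

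Fewer syndrome cases through fewer infections is also a real effect on incidence, so the downward pull is not purely bias. Counting M35.81 alone does not remove it, as the e = 0 case shows. The two worked values with extra cases, 2.50 and 1.20, both stay below the 3.0 signal threshold, so the added definition would not have changed the signal decision in those scenarios.

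Finally, this version is dated 18 March 2026 and the final report is planned for 30 April 2026. Replacing a pre-specified definition so late is hard to defend. Adding one is not.

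**Conclusion.** The point holds for the counting rule. Cases coded M35.81 without U07.1 are scored event-free in both designs, and an increase confined to them cannot be detected. This follows from the code list alone and needs no assumption.

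The shift in the ratio is a narrower matter. It concerns the primary Phase 2 comparison and comparisons with comparators who had no COVID-19 vaccine at entry. There the ratio would tend to fall below 1, for example to 0.50 at v = 0.5 and m = 0, or 0.59 at m = 0.3. These sizes rest on assumed v and m, equal protection from other vaccines, and counted cases that follow COVID-19 incidence. They illustrate the effect and do not predict it. No direction can be claimed for the SCRI.

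One of the 20 listed outcomes is affected. A null or low ratio would not exclude harm in patients without a recorded COVID-19 diagnosis, and the protocol does not say so.

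**What to change.** - Keep the current CBER BEST-based definition as it stands.
- Add a second definition for both designs, in the inpatient or emergency setting: M35.81 alone, or U07.1 together with M35.8 or M35.89.
- Report M35.81 cases split by presence or absence of U07.1, with the rule for linking the two codes in time stated. The split keeps the infection-associated share visible, which the second definition alone would not do.
- Apply the Section 9.3.2 record-review rule (rate ratio above 3.0 with P below 0.01) to the second definition.
- If results have already been seen, label this as an added analysis.
- State in Section 9.9 that the result requiring U07.1 cannot exclude harm without a recorded COVID-19 diagnosis.

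The cost is one further code-list entry, one extra outcome run in each design and a short limitation statement. The added definition will admit some less specific cases, and keeping the current one alongside it preserves comparability with its source.
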